#### 1.4 **List of Abbreviations**

Abbreviation	Definition
AE	adverse event
ALT	alanine aminotransaminase
AST	aspartate aminotransaminase
BID	bis en die, twice a day
BUN	blood urea nitrogen
CFR	Code of Federal Regulations (United States)
CKD	chronic kidney disease
CRO	contract research organization
ECG	electrocardiogram
eCRF	electronic case report form
EDC	electronic data capture
ePRO	electronic patient-reported outcome
ESRD	end-stage renal disease
FAS	Full Analysis Set
FDA	(United States) Food and Drug Administration
FSH	follicle-stimulating hormone
GCP	Good Clinical Practice
GI	gastrointestinal
HD	hemodialysis
HDPE	high-density polyethylene
IB	Investigator's Brochure
IBS-C	irritable bowel syndrome with constipation
ICF	informed consent form
ICH	International Committee on Harmonization
IEC	Independent Ethics Committee
iFGF23	intact fibroblast growth factor 23
IRB	Institutional Review Board
IRT	Interactive Response Technology
ITT	intent-to-treat
IUD	intrauterine device
Kt/V	a measure of dialysis adequacy
MedDRA	Medical Dictionary for Drug Regulatory Activities

23 February 2021 CONFIDENTIAL Page 18 of 60

Ardelyx, Inc. Protocol Number: TEN-02-402 Edition No. 2

Abbreviation	Definition
NHE3	sodium-hydrogen exchanger 3
PD	peritoneal dialysis
PR	ECG interval from P wave onset to QRS complex onset
PTH	parathyroid hormone
QD	quaque die, once a day
QRS	principal deflection in ECG
QT	ECG interval
QTc	QT interval which has been corrected by taking into account heart rate
RBC	red blood cell
RR	ECG interval between two consecutive R waves
SAE	serious adverse event
SAP	statistical analysis plan
SOP	standard operating procedure
s-P	serum phosphorus
TID	ter in die, three times a day
WBC	white blood cell count

CONFIDENTIAL 23 February 2021 Page 19 of 60

Protocol Number: TEN-02-402

Edition No. 2

## 2 INTRODUCTION AND BACKGROUND

#### 2.1 Introduction

Chronic kidney disease (CKD) affects 5-10% of the population globally and the numbers of patients suffering from end-stage renal disease (ESRD) are increasing (Eknoyan 2005). With progressing impairment of renal function, the ability of the kidneys to appropriately excrete phosphate is reduced and hyperphosphatemia is a nearly universal complication of ESRD. Hyperphosphatemia is also part of the CKD bone mineral disorder, which is associated with a disruption of normal serum and tissue concentrations of phosphorus and calcium, and changes in circulating levels of hormones such as parathyroid hormone (PTH) and vitamin D. Left untreated, hyperphosphatemia can lead to vascular and tissue calcifications, bone pain, fractures, and worsening secondary hyperparathyroidism and is associated with increased cardiovascular morbidity and mortality. Observational data show that treatment with phosphate binders to reduce hyperphosphatemia is independently associated with improved survival (Waheed 2013). Experimental studies provide support for the epidemiologic findings: phosphate excess promotes vascular calcification, induces endothelial dysfunction and may contribute to other emerging CKD-specific mechanisms of cardiovascular toxicity (Waheed 2013). Hence, clinical treatment guidelines for patients with advanced kidney disease suggest maintaining serum phosphorus (s-P) within 3.5 to 5.5 mg/dL, which is close to the normal range (KDIGO Guideline 2009).

In addition to dietary phosphorus restrictions and dialysis, 80-90% of ESRD patients need treatment with oral phosphate binders. Despite widespread use of phosphate binders, a large proportion of patients do not achieve adequate phosphorus control (DOPPS Practice Monitor 2018). The binding mechanism requires frequent dosing and often, many large pills in order to bind enough dietary phosphorus, and tends to be associated with a significant number of gastrointestinal (GI) side effects including bloating, constipation and nausea. Effectively treated hyperphosphatemia with binders is extremely difficult because of the considerable burden that binders place on patients. In addition to the pill burden and dosing frequency associated with all phosphate binders, the side effect profile with poor GI tolerability and concerns for long-term negative effects such as tissue calcification, and potential metal accumulation toxicity from calcium-based and metal-based binders, respectively, further impair effective phosphorus control in ESRD patients. There is, therefore, an unmet medical need to develop oral phosphate-lowering medications with new mechanisms of action, a more manageable dosing and administration regimen, and improved risk-benefit profile.

23 February 2021 CONFIDENTIAL Page 20 of 60

Protocol Number: TEN-02-402

Edition No. 2

Tenapanor is an oral, essentially non-absorbed, locally acting inhibitor that targets the sodium/hydrogen exchanger 3 (NHE3), an antiporter expressed on the apical surface of the epithelium of the small intestine and colon. Inhibition of NHE3 by tenapanor results in reduced sodium absorption and consequently, proton retention in cells. This modest intracellular proton retention induces a conformational change in claudin proteins present in tight junctions, reducing permeability specific to phosphate.

[figure not shown]
Tenapanor reduces intestinal phosphate absorption, predominantly through reduction of passive paracellular phosphate influx, the most important overall mechanism of intestinal phosphate absorption. Tenapanor modulates tight junctions to increase the transepithelial electrical resistance, thereby reducing paracellular phosphate permeability; this effect is mediated exclusively via on-target NHE3 inhibition. Blocking NHE3 by tenapanor has no observed effect on serum sodium, nor on the absorption of ions, nutrients, or macromolecules other than dietary sodium and phosphorus.

Results from three Phase 3 studies have demonstrated the efficacy of tenapanor in decreasing s-P levels in adult CKD patients on dialysis with hyperphosphatemia, as both a monotherapy and as a dual-mechanism approach with phosphate binders.

Tenapanor (IBSRELA®) has been approved for the treatment of irritable bowel syndrome with constipation (IBS-C). Tenapanor has been administered to greater than 2800 people including healthy volunteers, patients with IBS-C, CKD with Type 2 diabetes mellitus, and CKD on dialysis. Tenapanor has been evaluated in short term studies up to 900 mg/day and for >20 months at 60 mg/day.

## 2.2 Description of Investigational Product

Tenapanor is a GI-acting, minimally systemic, NHE3 inhibitor. Tenapanor is administered as the hydrochloride salt and is chemically described as: (S)-N,N'-(10,17-dioxo-3,6,21,24-tetraoxa-9,11,16,18-tetraazahexacosane-1,26-diyl)bis(3-((S)-6,8-dichloro-2-methyl-1,2,3,4-tetrahydroisoquinolin-4-yl) benzenesulfonamide) dihydrochloride. Its empirical formula is  $C_{50}H_{68}Cl_6N_8O_{10}S_2$ .

23 February 2021 CONFIDENTIAL Page 21 of 60

Protocol Number: TEN-02-402

Edition No. 2

Dosing consists of one 10 mg, 20 mg or 30 mg tablet, taken orally BID just prior to breakfast and dinner (but not prior to the meal immediately prior to hemodialysis).

Tenapanor tablets, 10 mg, 20 mg and 30 mg, are packaged in an induction sealed, opaque white high-density polyethylene (HDPE) bottle (20 tablets/bottle) with a white polypropylene child resistant closure and a desiccant canister. Tablets of tenapanor should be stored in the original packaging according to the labeling.

# 2.3 Study Rationale

Tenapanor is an investigational product being evaluated for its ability to control s-P levels in adult patients with CKD on dialysis. Most CKD patients on dialysis currently take phosphate binders to control s-P levels. A significant proportion of ESRD patients still do not achieve adequate phosphate control (DOPPS Practice Monitor 2019). Since tenapanor lowers s-P levels via a different mechanism of action, it is believed that tenapanor as monotherapy or combined with current phosphate binder therapy will produce additional phosphorus-lowering activity. This study is designed to investigate different methods of initiating tenapanor therapy in CKD patients on dialysis with hyperphosphatemia.

#### 2.4 Risk-Benefit Assessment

The risk-benefit assessment of tenapanor is based on nonclinical toxicology, safety, and pharmacology studies as well as 25 clinical trials conducted with tenapanor. Results from the risk-benefit assessment are described in the Investigator's Brochure (IB).

Nonclinical toxicological studies of up to 9 months have been conducted in rodents and dogs. The toxicological profile includes soft stools and/or diarrhea and findings secondary to dehydration; these findings are an expected manifestation of the compound's exaggerated pharmacologic activity and findings were reversible during the recovery period without medication. A two-year carcinogenicity study in Sprague-Dawley rats was negative.

The safety, tolerability, pharmacodynamics, and efficacy of tenapanor have been evaluated in greater than 2800 people including healthy volunteers, patients with IBS-C, CKD with

23 February 2021 CONFIDENTIAL Page 22 of 60

Protocol Number: TEN-02-402

Edition No. 2

Type 2 diabetes mellitus, and CKD on dialysis. Tenapanor has been evaluated in short-term studies up to 900 mg/day and for >20 months at 60 mg/day.

Tenapanor has minimal systemic bioavailability. Less than 1% of plasma pharmacokinetics samples collected during human studies (>3000 samples) have quantifiable tenapanor present in blood plasma (lower limit of quantification = 0.5 ng/mL); all samples with quantifiable tenapanor were below 1.5 ng/mL.

The reduction in sodium uptake results in an increase in net fluid volume in the intestinal tract. Based on this mechanism of action, tenapanor has the potential to produce softer or looser stools and increase stool frequency. Tenapanor has been demonstrated to be generally safe and well tolerated in clinical studies. The safety profile with softening or loosening of stool consistency and GI adverse events (AEs) have been consistent with its pharmacology.

The theoretical AEs from tenapanor treatment in CKD patients on dialysis would be due to exaggerated pharmacological effects and may include electrolyte disturbances, metabolic acidosis, soft stools/diarrhea, and reduced blood pressure. While a softening or loosening of the stool with an increased fluid loss via the intestine is an intended and desired effect of tenapanor in some patients, sensitive patients should be monitored for signs of dehydration in case of prolonged severe diarrhea. This study protocol includes clinical laboratory tests and vital signs. The health status of each patient will be checked at each visit. All patients will continue their existing treatment with phosphate binders when their participation in the study ends. See the IB for details on non-clinical and clinical results with tenapanor.

Patients will be informed both verbally and in writing about these aspects before taking part in any study-specific examination. The study will be conducted under conditions that ensure a high probability for the early detection of untoward events and for appropriate intervention.

In summary, risks to participants in this short-term study are considered acceptable. Results from this study will be important for the potential use of this new therapy, which could improve the treatment of hyperphosphatemia in ESRD patients.

## 3 STUDY OBJECTIVES

## 3.1 Primary Objective

The primary objective of this study is:

• To evaluate the effect of tenapanor alone or in combination with phosphate binders to achieve target serum phosphorus (s-P) levels of ≤5.5 mg/dL when tenapanor is

23 February 2021 CONFIDENTIAL Page 23 of 60

Protocol Number: TEN-02-402

Edition No. 2

administered as the core therapy (alone or in combination with phosphate binder) for the treatment of hyperphosphatemia in patients with CKD on dialysis.

## 3.2 Secondary Objectives

The secondary objectives of this study, for the treatment of hyperphosphatemia in CKD patients on dialysis who are phosphate binder naïve or on phosphate binder therapy, include:

- To evaluate the effect of tenapanor alone or in combination with phosphate binders to achieve various s-P levels (e.g., ≤4.5 mg/dL).
- To evaluate different strategies of initiating tenapanor for the control of s-P level.
- To evaluate the effect of different strategies of initiating tenapanor on stool frequency and consistency using a daily eDiary.
- To evaluate the effect of tenapanor on reducing daily phosphorus-lowering therapy pill burden (number of pills and total pill weight) when patients are started on or transitioned to tenapanor from current phosphate binder therapy.
- To evaluate the impact of patient education and use of standard of care medication on the tolerability management of tenapanor.
- To evaluate the tolerability of tenapanor when patients are started on or transitioned to tenapanor from current phosphate binder therapy.
- To evaluate patient experience with phosphorus management routine during study compared to before study.
- To evaluate the effect of tenapanor alone or in combination with phosphate binders on iFGF23 and PTH.
- To evaluate the effect of tenapanor alone or in combination with phosphate binders on the use of PTH-modifying medications.

## 4 STUDY DESIGN

## 4.1 Design Summary

This is a randomized, open-label study to evaluate different methods of initiating tenapanor therapy in CKD patients on dialysis with hyperphosphatemia, when they are either phosphate binder naïve or on phosphate binder therapy. The study consists of a Screening visit, a 10-week open-label Treatment Period (Part A), and an optional 16-week open-label Extension Period (Part B), with a total of three cohorts of patients as shown in Figure 4-1:

• Patients with s-P >5.5 and ≤10.0 mg/dL under stable phosphate binder treatment regimen are randomized in a 1:1 ratio to two different treatment cohorts:

[figure not shown]
23 February 2021 CONFIDENTIAL Page 24 of 60

Protocol Number: TEN-02-402

Edition No. 2

- Cohort 1 (straight switch), which stops taking phosphate binders and is immediately started on tenapanor 30 mg twice daily (BID) at Visit 2 (Day 1);
- Ochort 2, which decreases phosphate binder dose by at least 50% (may be more than 50% if patient is taking an odd number of binder pills each day), with ability to switch the binder regimen from thrice daily (TID) to BID or QD; and initiates tenapanor 30 mg BID at Visit 2 (Day 1).
- Phosphate binder naïve patients with s-P >4.5 and ≤10.0 mg/dL are enrolled as Cohort 3 and receive tenapanor at Visit 2 (Day 1) with a starting dose of 30 mg BID.

Figure 4-1: Study Design Diagram

a Day 1 is the randomization/enrollment day and serves as the reference day for all visits.

The Screening visit (Visit 1) must be scheduled at the first short dialysis interval of the week (Wednesday or Thursday), the Randomization/Enrollment visit (Visit 2) must be scheduled two days after the Screening visit at the second short dialysis interval of the week (Friday or Saturday), and all other visits in the study must be scheduled after a short dialysis interval (Wednesday or Friday for patients on a Monday-Wednesday-Friday schedule and Thursday or Saturday for patients on a Tuesday-Thursday-Saturday schedule). Body weight, vital signs, and blood collections for laboratory assessments must be performed pre-dialysis (prior to dialysis at the visit). All other assessments may be performed pre-, during, or post-dialysis but should be performed at the same time at each visit and the same day as dialysis.

The enrollment criteria on s-P will be evaluated based on the s-P measured at the Screening visit (Visit 1) alone (Cohort 3 only: binder naïve) or together with the most recent s-P measurement prior to the Screening visit (Visit 1):

23 February 2021 CONFIDENTIAL Page 25 of 60

Protocol Number: TEN-02-402

Edition No. 2

• Patients on phosphate binder therapy must receive phosphate binder(s) thrice daily, and both the s-P level assessed at the most recent measurement prior to the Screening visit (Visit 1) and the s-P level assessed at the Screening visit (Visit 1) must be >5.5 and ≤10.0 mg/dL to qualify for randomization into Cohort 1 or Cohort 2 at Visit 2 (Day 1).

Phosphate binder naïve patients must have the s-P level assessed at the Screening visit
(Visit 1) >4.5 and ≤10.0 mg/dL to qualify for enrollment into Cohort 3 at Visit 2
(Day 1).

Patients who do not meet the randomization/enrollment criteria on s-P will be discontinued as screen failures. Patients must continue to meet all other applicable inclusion/exclusion criteria at Visit 2 (Day 1) in order to be randomized into Cohort 1 or Cohort 2 or be enrolled in Cohort 3.

Patients will be educated at Screening (Visit 1) and Randomization/Enrollment (Visit 2) about tenapanor, how to take tenapanor, what they may experience on tenapanor, medications to be discontinued before starting tenapanor, and how best to manage a possible increase in bowel movement frequency and/or loose stool if bothersome (e.g., use of over-the-counter anti-diarrheal), etc.

In order to assess the tolerability profile of tenapanor alone or combined with phosphate binders, patients will use a daily eDiary to record daily bowel habits (stool frequency and stool consistency) throughout the 10-week Treatment Period.

On Day 1 (Visit 2), patients will start to receive tenapanor at a dose of 30 mg BID. Tenapanor will be taken orally BID; just prior to breakfast and dinner. Patients should **not** take study drug at the meal immediately preceding hemodialysis. The Investigator may titrate the dose of tenapanor in 10 mg increments down to a minimum of 10 mg QD or up to a maximum of 30 mg BID at any time during the study based on s-P levels and/or GI tolerability.

If a phosphate binder is being taken by a patient in any of the three cohorts, it can be dosed starting at either QD, BID or TID: if taken QD, it should be taken with the largest meal of the day; if taken BID, it should be taken with the same meals tenapanor is taken with. The Investigator may decrease the dose of phosphate binder at any time during the study based on s-P levels. However, dose up-titration for phosphate binder is not allowed from Day 1 (Visit 2) until Week 2 of the Treatment Period (Visit 4). Starting from Visit 4, the Investigator may

23 February 2021 CONFIDENTIAL Page 26 of 60

Protocol Number: TEN-02-402

Edition No. 2

increase the dose of phosphate binder or add phosphate binder based on s-P levels; the dose of a phosphate binder can be titrated up to the maximum dose TID per the corresponding phosphate binder package insert, if needed, based on s-P levels.

If decreasing the dose of tenapanor or phosphate binder due to low s-P levels, the phosphate binder dose should be decreased prior to decreasing the tenapanor dose until patient is no longer taking any phosphate binder. If increasing the dose of tenapanor or phosphate binder due to high s-P levels, the tenapanor dose should be increased prior to increasing the phosphate binder dose until the tenapanor dose reaches 30 mg BID or cannot be increased due to GI tolerability at the Investigator's discretion. Details of recommended dose adjustments based on s-P levels are provided in Section 6.1.4.

Safety assessments will be performed at various time points throughout the study and will include physical examination, body weight, vital signs, safety laboratory tests, 12-lead electrocardiogram (ECG), and AE recording. Stool frequency and stool consistency will be collected using a daily eDiary throughout the 10-week Treatment Period (Part A only) as tolerability measures.

Blood samples will be collected to measure s-P, iFGF23, PTH, and clinical laboratory chemistry and hematology tests; additional samples will be stored, as appropriate, for the potential evaluation of exploratory biomarkers.

Approximately 300 CKD patients on dialysis and stable phosphate binder therapy will be randomized in a 1:1 ratio to Cohort 1 or Cohort 2 (~150 patients/cohort); and approximately 30 phosphate binder naïve patients with CKD on dialysis will be enrolled into Cohort 3. Overall, approximately 330 patients will be randomized or enrolled at approximately 40 sites in the United States.

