 The daily eDiary will ask questions about a patient's stool frequency and stool consistency during the past 24 hours. The eDiary is completed during Part A of the study.

23 February 2021 CONFIDENTIAL Page 16

b All visits are after a short interval (Wednesday or Friday for M,W,F dialysis and Thursday or Saturday for T, Th, S dialysis)

c All assessments and procedures at Visit 9 except study dispensing should be performed at the Early Termination visit for patients who prematurely discontinue from the study before Visit 9; those at Visit 13 should be performed at the Early Termination visit for patients who prematurely discontinue from the study between Visit 9 and Visit 13, if possible.

d Day 1 is the randomization/enrollment day and serves as the reference day for all post-randomization visits.

e Patients must continue to meet all applicable inclusion/exclusion criteria before randomization/enrollment, including the criteria based on the s-P level at Visit 2.

f Record only changes to medical history from Visit 1

g Refer to Appendix I for a list of medications to be discontinued before starting tenapanor, prohibited concomitant medications, PTH-modifying medications, and medications recommended for managing changes in bowel movements during the study. These medications will be checked at every visit. Any new PTH-modifying medication use or changes to existing PTH-modifying medication use need to be adequately recorded in the Prior/Concomitant Medications eCRF.

h Patient education will include information about tenapanor, how to take tenapanor, what they may experience on tenapanor, medications to be discontinued before starting tenapanor, and how best to manage a possible increase in bowel movement frequency and/or loose stool if bothersome (e.g., use of over-the-counter anti-diarrheal), etc.

Protocol Number: TEN-02-402

Edition No. 2

- j Vital signs include sitting or supine blood pressure and pulse, prior to dialysis at the visit.
- k Safety laboratory evaluations will include the hematology and serum chemistry tests.
- FSH (postmenopausal females) and pregnancy tests are performed on all females <60 years of age unless there is a documented method of sterilization, or FSH test confirms postmenopausal status.

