#### 7.5 Efficacy Endpoints

Efficacy measures in this study include s-P (to be measured at all scheduled visits except Visit 2), iFGF23, PTH, medication dose, pill number, pill weight, and other information relative to drug usage (e.g., % on monotherapy), and patient experience.

The following efficacy endpoints will be analyzed by cohort and for the entire FAS at each post-baseline visit (only for s-P endpoints), the endpoint visit of the Treatment Period, and the endpoint visit of the entire study:

23 February 2021 CONFIDENTIAL Page 43 of 60

Protocol Number: TEN-02-402

Edition No. 2

- s-P response: achieving or maintaining s-P  $\leq$  5.5 mg/dL
- Normal s-P response: achieving s-P ≤4.5 mg/dL
- Borderline s-P response: achieving or maintaining s-P ≤6.5 mg/dL
- Change from baseline in s-P
- Relative change from baseline in iFGF23, derived as "change from baseline in iFGF23/baseline iFGF23"
- Change from baseline in PTH
- Change from baseline in total daily dose of PTH-modifying medications (mg)

The following efficacy endpoints will also be analyzed by cohort and for the entire "FAS (Cohorts 1-2)" at each post-baseline visit, the endpoint visit of the Treatment Period, and the endpoint visit of the entire study:

- Change from baseline in total daily dose of phosphorus-lowering medication (mg) (tenapanor and phosphate binder combined)
- Change from baseline in total daily pill weight (tenapanor and phosphate binder combined)
- Change from baseline in total daily pill number (tenapanor and phosphate binder combined)
- Medication dose response: achieving at least 30% reduction from baseline in total daily dose (mg) of phosphorus-lowering medication
- Pill weight response: achieving at least 30% reduction from baseline in total daily pill weight
- Pill number response: achieving at least 30% reduction from baseline in total daily pill number (e.g., reduce from 6 pills at baseline to ≤4 pills and reduce from 9 pills at baseline to ≤6 pills)
- Pill burden response: achieving pill weight response and pill number response
- s-P and medication dose response: achieving s-P response and medication dose response
- s-P and pill weight response: achieving s-P response and pill weight response
- s-P and pill number response: achieving s-P response and pill number response
- s-P and pill burden response: achieving s-P response, pill weight response, and pill number response

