#### 9.4.6 Visit Windows

No analysis visit windows will be formally defined. The schedule of assessments and procedures in Section 1.3 details the intended collection of study variables at specified visits. Data collected at a scheduled visit will be used as the data at the corresponding analysis visit even if the visit is out-of-window. To minimize the amount of missing data, data collected at an unscheduled visit will be mapped to an analysis visit based on analysis windows if data at the corresponding scheduled visit are not available. Similarly, data from the Early Termination visit may also be mapped. Detailed information on analysis windows will be provided in the SAP.

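### For hemodialysis patients, baseline s-P is fixed at the first short dialysis interval while Table 1-1 follow-up defaults to the second, so a within-week difference could enter change from baseline

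*Combined protocol and SAP*

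**What the plan says.** Section 4.1 ties Visit 1 to the first short interval of the dialysis week: "The Screening visit (Visit 1) must be scheduled at the first short dialysis interval of the week (Wednesday or Thursday"). Visit 2 "must be scheduled two days after the Screening visit at the second short dialysis interval of the week (Friday or Saturday"). Table 1-1, footnote d, states: "Day 1 is the randomization/enrollment day and serves as the reference day for all post-randomization visits".

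For later visits the rule is looser: "all other visits in the study must be scheduled after a short dialysis interval", and either short interval is allowed (Wednesday or Friday on a Monday-Wednesday-Friday schedule, Thursday or Saturday on a Tuesday-Thursday-Saturday schedule). The windows are ±2 days in Part A and ±7 days in Part B. Laboratory blood must be drawn before dialysis.

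Section 7.5 lists "s-P (to be measured at all scheduled visits except Visit 2") among the efficacy measures. Section 7.3.5.1 takes the last value before the first dose as the laboratory baseline, so the planned s-P baseline is the Visit 1 value.

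Under Section 9.4.6, if a scheduled value is missing, "data collected at an unscheduled visit will be mapped to an analysis visit based on analysis windows". The windows themselves are left to the separate SAP. Section 9.4.5 names the two stratification factors, and possibly the baseline value, as covariates. It does not name the day or interval of the draw.

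**The concern.** By confining s-P draws to short intervals, the protocol treats timing within the dialysis week as relevant. It then fixes baseline at one short interval and, by the visit calendar, sets follow-up by default at the other. By Friday or Saturday a hemodialysis patient has had one more session since the long interval than on Wednesday or Thursday.

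If s-P differs between those two days for any reason other than drug, the difference becomes part of change from baseline at every affected visit. All three cohorts receive tenapanor and the analysis is mainly descriptive by cohort, so nothing in the design would show how much of a change is due to draw day. The ≤5.5 mg/dL response, which carries the primary objective, is read on the follow-up day, while entry to Cohorts 1 and 2 requires more than 5.5 mg/dL at Visit 1.

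**Working it through.** **1. Which draws exist.** Table 8-1 plans 12 phosphorus samples per patient. Table 1-1 gives Visit 1 (1) + Visits 3 to 9 (7) + Visits 10 to 13 (4) = 12. The figure is reproduced with no draw at Visit 2, in agreement with Section 7.5. Footnote e of Table 1-1 nevertheless refers to an s-P criterion at Visit 2.

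**2. Weekdays in Table 1-1.** With Day 1 on Friday (or Saturday) and no Day 0, a visit falls on the same weekday as Day 1 when Day − 1 is a multiple of 7.

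| Nominal day | 8 | 15 | 22 | 29 | 43 | 57 | 71 | 99 | 127 | 155 | 183 |
|---|---|---|---|---|---|---|---|---|---|---|---|
| (Day − 1)/7 | 1 | 2 | 3 | 4 | 6 | 8 | 10 | 14 | 18 | 22 | 26 |

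All 11 are whole weeks, so all fall on Friday or Saturday. Baseline, at Day -2, falls on Wednesday or Thursday.

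**3. What the windows allow.** For Visit 3 (Days 6 to 10), a Monday-Wednesday-Friday patient has two compliant days: Day 6 (Wednesday) and Day 8 (Friday). A Tuesday-Thursday-Saturday patient has Day 6 (Thursday) and Day 8 (Saturday). The other Part A visits repeat this pattern. In Part B both intervals lie well inside ±7 days; around Day 99, for example, Days 97 and 104 are Wednesdays.

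**4. The other Part B schedule.** Sections 8.7 and 8.8 give Days 101, 131, 161 and 191. The remainders of (Day − 1)/7 are 2, 4, 6 and 1, so these days are Sunday, Tuesday, Thursday and Saturday for Monday-Wednesday-Friday patients, and Monday, Wednesday, Friday and Sunday for Tuesday-Thursday-Saturday patients. None is a dialysis day on the patient's own schedule. The Friday/Saturday default in Part B therefore holds for Table 1-1 only.

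**5. Size in mean change.** Let d be the Wednesday/Thursday minus Friday/Saturday difference in s-P without drug effect, and p the share of follow-up draws on Friday/Saturday. The bias in mean change for hemodialysis patients is −p × d. The values of d are assumptions.

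| d (mg/dL) | p = 1 | p = 0.5 |
|---|---|---|
| 0 | 0 | 0 |
| 0.1 | −0.10 | −0.05 |
| 0.2 | −0.20 | −0.10 |
| 0.3 | −0.30 | −0.15 |
| −0.3 | +0.30 | +0.15 |

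For scale, with about 150 patients and an assumed SD of 1.3 to 2.0, the standard error of a mean is 1.3/√150 = 0.106 to 2.0/√150 = 0.163.

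**6. Response rates.** Suppose 40% would be at or below 5.5 mg/dL on the Wednesday/Thursday scale (assumed), with normal values and the same SD range. The Friday/Saturday rate is Φ(Φ⁻¹(0.40) + d/SD). At p = 1 this gives 41.9 to 43.0% for d = 0.1, 43.9 to 46.0% for d = 0.2 and 45.9 to 49.1% for d = 0.3. The 95% half-width at n = 150 is 1.96 × √(0.40 × 0.60/150) = 7.8 points. These are rates on a different draw day. No baseline is subtracted.

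**7. Cohort 1 versus Cohort 2.** With the same p in both cohorts, the −p × d terms cancel in the difference of mean changes. Mixing days adds little noise: at d = 0.3 and p = 0.5 the added variance is 0.3² × 0.25 = 0.0225. Against an assumed 1.5² = 2.25 this is 1% of the variance, or about 0.5% on the standard error.

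**The case against.** The strongest answer is that the documents nowhere say that s-P differs between the two short intervals. The scheduling rule separates short from long intervals and treats the two short ones as interchangeable. The long-interval contrast is thus already removed, and all draws are pre-dialysis. This stands as far as it goes: size and sign are unknown, and zero is possible. It does not explain why baseline alone is tied to one interval.

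A reader might infer more than the documents support:

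- *That tenapanor's effect is overstated.* This needs a fall in s-P from the first to the second short interval, which the documents do not state. A rise would understate the effect.
- *That follow-up is always on Friday or Saturday.* Section 4.1 expressly permits Wednesday or Thursday, and Sections 8.7 and 8.8 give other Part B days. The mismatch is a default.
- *That the response rates carry a baseline bias.* They are absolute thresholds at the visit, and nothing makes Wednesday/Thursday the correct scale. Draw day matters there only through the day itself and the Wednesday/Thursday entry criterion.
- *That the mapping rule admits post-dialysis values.* Sections 4.1 and 7.3.5 already require pre-dialysis draws. Only the interval is left open, and the windows are deferred to the SAP.

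Peritoneal dialysis patients are eligible, and the interval argument does not apply to them.

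**Conclusion.** The point holds as a possible systematic offset in within-cohort change from baseline in s-P for hemodialysis patients. It rests on the Table 1-1 calendar, the absence of a Visit 2 draw, and the lack of a tenapanor-free arm or stated draw-day adjustment. Under the assumed differences of 0 to 0.3 mg/dL, the bias is 0 to 0.3 mg/dL if all follow-up draws fall on Friday/Saturday. Over a whole cohort it shrinks in proportion to the share of hemodialysis patients, which the documents do not give.

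The upper end of that range exceeds the standard errors in the working, so it could matter for a descriptive reading of change. The randomized comparison of mean change is not threatened in expectation. This is an inexpensive improvement to the plan and does not make the study uninterpretable.

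**What to change.** For hemodialysis patients, choose one of two routes:

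- Target post-baseline s-P draws to the Visit 1 interval. In Part A this is the nominal day minus 2 (Days 6, 13, 20, 27, 41, 55, 69), already permitted. Do the same in Part B.
- Add a pre-dose, pre-dialysis s-P at Visit 2 as a matched Friday/Saturday baseline, and keep the Visit 1 value for eligibility, stratification and pairing with any Wednesday/Thursday follow-up. State the pairing explicitly: under Section 7.3.5.1 the Visit 2 value would otherwise become the baseline for every draw, and Wednesday/Thursday follow-up would then be mismatched.

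Under either route, and also if visits have already taken place:

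- Derive the interval (first short, second short, long) for each s-P from the visit date and the dialysis schedule.
- Report change from baseline like-for-like by draw interval as a sensitivity analysis. With a Visit 1 baseline only, this means the Wednesday/Thursday draws.
- In the SAP, map unscheduled s-P values only if drawn after a short interval.

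Reconcile the Part B days (Table 1-1: 99/127/155/183; Sections 8.7 and 8.8: 101/131/161/191), and footnote e's reference to a Visit 2 s-P that is not scheduled.

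Cost: the first route reduces sites' scheduling freedom, since the target sits at the window's edge. It also moves Visit 4, to which dose-adjustment rules are linked, and the sponsor must reconcile that timing. The second route costs one 4 mL sample, raising the Table 8-1 total from 135 to 139 mL. The analysis changes need no extra visit or sample.
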